## **8. Research Setting**

- 8.4. Patients interested in participating in the study will be gided by a Clinical Research Coordinator who will collect information from the Brief Pain Inventory (short form) questionnaire and will also collect and store a blood sample for assay at the termination of the project period.
- 8.5. All patients will be recruited from the UNMH Pain clinic and examined by [name] (co-I).
- 8.6. All research procedures will be conducted in the CTSC clinical laboratory. All analytics will be conducted in the Center for Molecular Drug Discovery, a CTSC translational lab directed by [name] (co-I).
- 8.7. A community advisory board will not be involved
- 8.8. No research will be conducted outside of UNMH and UNM-CTSC

## **9. Resources Available**

- 9.4. The PI and study staff have received training for clinical trials. [name] (PhD) is a basic scientist conducting the cell assays and interpreting the data results. [name](PhD) is a basic scientist directing the CTSC core for conducting the cell assays and interpreting the resultant data. [name] (PhD) is a statistician and familiar with clinical trials designs, and [name] (MD) is a physician who specialized in pain treatment at the UNMH Pain Clinic.
- 9.5. [name], MD will be responsible for medical decision-making and ordering and evaluation of necessary diagnostics and therapeutics.
- 9.6. [name] treats 15-30 patients daily at the UNMH Pain Clinic. With this high access to patients, the goal of enrolling 30 patients during an 11 month period is predicted to be very feasible.

All 30 recruited patients will be needed with no further screening.

An estimated 6 hrs per patient will be devoted to consent, completing surveys, blood draw, scheduling and dispensing the pramipexole or placebo by the Clinical Research Coordinator.

- The facilities used will be at the CTSC where consent, enrollment, scheduling visits, obtaining blood samples, completion of the Brief Pain Inventory survey, dispensing drugs at initiation and at midterm (end of week 2,) and collecting unused drug at termination. For the biological assays from human cell lines or from blood samples, the clinical laboratory arm of the CTSC, Center for Molecular Drug Discovery, will be used.
- The availability of medical and/or psychological resources that subjects might need as a result of an anticipated consequences of the human research will be available by [name] or by referral from [name]. The anticipated consequences of the research will be (1) improved pain relief, (2) no change in pain relief, or (3) a worsening of pain. [name] will continue to monitor patients after the study is terminated, as these patients will continue to receive outpatient care from the pain clinic.
- All persons assisting with the research will have group meetings once every 3 months in the conference room in the Dept of Anesthesiology. Goals of each meeting will include research progress updates, preliminary findings of the pain scores derived from the Brief Pain Inventory, problems or unanticipated adverse events, how these adverse events were managed, and action items for continued progress or needed to adjust to potential changes. [name] will provide updates on his clinical observations from his pain patients, [name] will provide updates with regard to progress or impediments of cell assays, [name] will provide a summary of data collected from the cell based assay from Phase I (Specific Aim I) and [name] will provide input for preparation of appropriate statistical analysis, manuscript preparation and future NIH NIDA grant preparation should the data support the research hypothesis.
- If CTSC resources are being accessed, the signed CTSC resources attachment must be uploaded on the CTSC Submission page in Click.

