### **5. Number of Subjects**

- 5.4. All subjects will be recruited from the UNMH outpatient population from the UNMH Pain Center.
- 5.5. The target sample size is 30 subjects with complete data. The investigators may recruit up to 45 patients to allow for any dropouts.
- 5.6. All subject recruited will participate. There will be no screening after recruitment.

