### **6. Study Timelines**

#### *6.4. Describe:*

- The duration the subject will participate in the study is 4 weeks
- The duration anticipated to enroll all subjects may require 10-11 months
- The expected duration for the investigators to complete the study analyses will be 12 months, with most of the analysis occurring in the final months 11-12.

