## **7. Study Endpoints**

- 7.4. The primary endpoint is the paper-and-pencil survey, the Brief Pain Inventory. The secondary study endpoints will be mRNA and protein analysis from blood samples provided at the initiation and terminal of the study.
- 7.5. *Safety endpoints of the study will include the following: (1) Worsening of pain score or increased verbal dissatisfaction with pain relief, (2) sudden onset of sleep without warning, (3) intense urges, (4) hallucinations and/or psychotic-like behaviors, (5) fever, and (6) orthostatic hypotension. While the patients who experience these adverse events, dosing with pramipexole will require a 50% step-wise reduction over a period of two weeks. Given the maximal allowable dose is 0.75 mg, this prescribed step-wise reduction is well within the manufacturer's recommended tapering of pramipexole, which the recommended dose reduction is 0.375 per day.*
- 7.6. No exploratory endpoint are in the current study.

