The second track of safety monitoring will be an interim review conducted shortly (within one week) after enrollment of the 15th participant. All relevant study information, including but not limited to pain and dosage data, any adverse events identified in screening (regardless of CTCAE grade), and any direct adverse-event reports to investigator [name], will be included in this review. PI [name] will conduct this review with assistance from investigators [name] and [name]. The HRRC will be notified if adverse events of CTCAE grade  $\geq 2$  have been identified in three or more patients in the active (pramipexole) arm at the time of this review. As noted above, the HRRC will be notified within five business days of any adverse events of grade 3 or higher, regardless of timing with respect to this interim review.

Stopping rules: Enrollment will be at least temporarily suspended if any of the following conditions are met:

- Instructions from the HRRC to suspend or terminate enrollment.
- A second adverse event of CTCAE grade 3 or higher among study participants. As with any first one, this event would be reported to the HRRC.
- Any event that, in the opinion of the PI, represents substantial unanticipated risk (i.e. a risk not included in the FDA pramipexole package insert or consent documentation) to study participants.

After any suspension, enrollment would only be resumed on instructions from the HRRC.

If enrollment is suspended, study-related treatment will continue as normal for any active study participants, except in the case of the third (substantial unanticipated risk) bullet point above. If study enrollment is suspended for that reason, participants will be advised to taper off or terminate study drug use as soon as possible.

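### Preliminary primary-endpoint results go to the whole study team every 3 months during enrolment, with no requirement that they be pooled or masked

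*Combined protocol and SAP*

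**What the plan says.** Section 7.4: "The primary endpoint is the paper-and-pencil survey, the Brief Pain Inventory". Section 9 on the team meetings: "All persons assisting with the research will have group meetings once every 3 months". On their content: "Goals of each meeting will include research progress updates, preliminary findings of the pain scores derived from the Brief Pain Inventory". The agenda also covers adverse events and action items, and at the same meetings the pain physician "will provide updates on his clinical observations from his pain patients".

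On timing, Section 6.4 says "The duration anticipated to enroll all subjects may require 10-11 months" and "The duration the subject will participate in the study is 4 weeks". On size, Section 5.5 says "The target sample size is 30 subjects with complete data" and allows recruitment of up to 45.

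The Safety Monitoring Plan in Section 14 adds a separate review within one week of enrolling the 15th participant. The principal investigator conducts it with two other investigators. Its scope is all relevant information, "including but not limited to pain and dosage data", and it counts adverse events of grade 2 or higher in the active arm.

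Neither section says whether pain scores are pooled, masked or shown by arm. The only restriction on sharing interim results is in Section 27.4, and it concerns the subjects, not the staff.

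**The concern.** The primary endpoint is self-reported pain, so it is sensitive to expectation. The pain physician identifies candidates and asks the three screening questions about satisfaction with relief (Section 4.1). The coordinator obtains consent (Section 24) and collects BPI scores at the weekly contacts (Section 14). If these people learn how the primary endpoint is running, and can connect it to treatment, they could change whom they approach and how they ask for scores in the subjects still to come. That would put the between-arm comparison at risk.

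Nothing in the plan is gained in exchange. The stopping rules in Section 14 concern safety and instructions from the review committee. No efficacy or futility rule draws on the BPI results shown at the meetings.

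**Working it through.** The plan gives no figure to reproduce here: it states no significance level, power or interim test for Phase II. The check is a count of meetings and subjects, followed by a reading of the safeguards.

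**Inputs.** Meetings every 3 months (Section 9); enrolment over M = 10 or 11 months and 4 weeks per subject (Section 6.4); N = 30 subjects, or up to 45 recruited (Section 5.5).

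**Assumptions.** Accrual is even, and meetings fall at months 3, 6 and 9 after enrolment opens. A week-4 score exists 28 days after entry, and 28/30.4 = 0.92 months.

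**Formulas.** Enrolled at month m = N × m / M. With a week-4 score at month m = N × (m − 0.92) / M. Share entering after the first meeting = 1 − 3/M.

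| N | M | Enrolled at months 3, 6, 9 | With week-4 score at months 3, 6, 9 |
|---|---|---|---|
| 30 | 10 | 9.0, 18.0, 27.0 | 6.2, 15.2, 24.2 |
| 30 | 11 | 8.2, 16.4, 24.5 | 5.7, 13.9, 22.0 |
| 45 | 10 | 13.5, 27.0, 40.5 | 9.4, 22.9, 36.4 |
| 45 | 11 | 12.3, 24.5, 36.8 | 8.5, 20.8, 33.1 |

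The share entering after the first meeting is 1 − 3/10 = 70% or 1 − 3/11 = 73%, whatever N is. Scores are collected weekly, so more subjects have some BPI data at each meeting than the last column shows.

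**Review after the 15th participant.** Still to enter: 30 − 15 = 15 subjects, or 45 − 15 = 30 if recruitment reaches its ceiling.

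**Could anyone at the meeting know allocation?**
- Section 4.1 has the coordinator use the randomization table as a template when dispensing drug.
- Sections 3.2 and 31 place dispensing with the pharmacy, also from a randomization table, and Section 3.2 does not say who is blinded.
- The Section 14 review needs adverse events attributed to the active arm, so the three people conducting it receive at least that much arm-level information, alongside pain data.
- Section 13 makes active and placebo capsules look identical at each dose level, which protects subjects and anyone without access to the table.

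Allocation knowledge within the team is therefore plausible, but it is not stated for the meeting.

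**The case against.** The strongest reply is that the bias is conditional. Subjects are randomised and capsules are matched. If the meeting sees only pooled scores and the staff are masked, a shift in whom they approach or in general optimism acts on both arms alike. It could affect generalisability or add noise, but it would not in itself bias the difference between arms. This stands, and it limits the point: a reader might infer that staff see unblinded efficacy results, but the text does not say so. What remains is that the plan does not require the safe version.

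Patients also score themselves. Section 12 has them complete paper forms, and Section 27.4 keeps study results from them. This lessens the risk but does not remove it, because staff still elicit scores. Sections 12 and 14 place telephone contact at weeks 1 and 3, and Section 13 describes it for all four weeks.

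Four stronger readings are tempting and not supported:

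- *The team steers the dose on the basis of these results.* Titration depends on whether relief is satisfactory (Section 14, Dose escalation risks), but no passage names who decides.
- *The plan shields the secondary endpoint better than the primary one, because blood samples are held to the end.* Section 12 gives its reason as avoiding a time-of-assay effect. That is batch control, not protection from interim knowledge.
- *The review after the 15th participant is another whole-team efficacy look.* It is a safety review by three investigators, and worsening pain is safety endpoint (1) in Section 7.5, so some pain data belong there.
- *The looks inflate the type I error.* No test is planned at any meeting.

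It is also fair to say that this is a small proof-of-concept trial and that the first meeting would have few week-4 scores, about 6 of 30. That bears on priority, not on whether the agenda item should stay.

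**Conclusion.** The point holds in a conditional form. The plan provides for preliminary results on a subjective primary endpoint to reach everyone on the study at about three meetings during open enrolment, with about 70% of subjects entering after the first. It contains no requirement to pool or mask, and no stated efficacy or futility decision needs the information. If results are seen by arm or by people who know allocation, later recruitment and score collection could be biased. If they are pooled and masked, the risk is much smaller. The documents do not settle which applies, and they do not show that bias will occur.

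The count rests on even accrual and on a first meeting three months after enrolment opens. The coordinator's presence follows from the statement that all persons assisting attend; that role is not listed separately. This is a cheap improvement, not a flaw that undermines the design.

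**What to change.** In Section 9, replace the agenda item on preliminary pain scores with the number of BPI forms due, received and complete. Add that no summary BPI results, by arm or pooled, are presented to staff who recruit, treat, dispense or collect BPI until the last week-4 visit is done.

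State the exception explicitly: individual subjects' scores stay available for weekly collection, safety and management as the protocol already provides. Without it, the sentence would bar staff from scores they handle every week.

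In the Section 14 review after the 15th participant, limit the pain data to what safety endpoint (1), worsening of pain, requires, with no comparison of mean BPI between arms.

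The cost is a few sentences and no change to any study procedure. The downside is that the team does not see efficacy trends during the study.

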## **10. Prior Approvals**

10.4. A waiver from IND from the FDA will not be required because pramipexole is FDA-approved for other indications (Restless Legs Syndrome, Parkinson's Disease), with no contraindications and no change in recommended dosing and route of delivery, and no increased risk to subjects.

10.5. The required Departmental Review Form signed by PIs Department Chair has been added.

10.6. N/A

10.7. The package insert for pramipexole has been attached.

## **11. Multi-Site Research**

11.4. This is not a multi-site study.

## **12. Study Procedures**

The goal of Phase II will be to determine the therapeutic benefit of pramipexole for pain, which is a repurposing of this FDA-approved drug with a good safety profile. In collaboration with [name] (co-I at UNMH Pain Clinic), patients from the UNM pain clinic will be recruited who are experiencing modest or suboptimal pain relief. The patient will meet the CTSC Clinical Research Coordinator, who will escort the patient to the Clinical Research Lab. At the time, an explanation of the study, consent, the Brief Pain Inventory survey will be completed, blood draw and Clinocard will be given to the patient (\$15/visit). Scheduling for the midterm visit to the CTSC (at the end of two weeks) will be determined. At the time of consent, all patients will be under standard pain treatment and will be randomized into two groups: (1) patients receiving pramipexole in addition to their standard ongoing pain treatment, or (2) no pramipexole but will continue to receive the standard pain treatment. Patients will be followed up in the morning at weekly intervals to provide pain scores either by phone (for week 1 and 3), or by return visit (for end of week 2 and at the end of week 4) until study termination which is at the end of week 4.. At the initiation of the study and at the end of 4 weeks, blood will be collected and analyzed for mRNA for TLR4, p38, NFKB, NLRP3-ASC, Caspase-1, IL-1 $\beta$ , TNF- $\alpha$ , HMGB1, and IL-10. The dose and route of administration of pramipexole will be identical to that previously approved for the treatment of Restless Legs Syndrome and according to manufacturer's recommended prescribing protocol (Mirapex, Boehringer Ingelheim Int. GmbH). Briefly, oral dosage will be titrated each week to achieve a weekly total daily dose of 0.125 (mg), 0.250, 0.5 or 0.750. Patients will take one capsule containing pramipexole or placebo 2-3 hours before bedtime.

Patient recruitment, assessment of Brief Pain Inventory (BPI): Pain scores and blood draws will be conducted at the CTSC Participant Clinical Interactions Unit with the CTSC Clinical Research Coordinator. Blood samples collected by the CTSC Clinical Research Coordinator will be analyzed at the Center for Molecular Discovery by personnel from [name] lab, trained by personnel from the Center for Molecular Drug Discovery (Director; [name], co-I). Personnel from the [name] lab have expertise in inflammatory marker analysis from PBMCs [57, 58]. All freshly collected blood samples will be frozen and stored by the Clinical Research Coordinator at the CTSC Clinical Laboratory and will be transported to the Center for Molecular Drug Discovery once ALL of the samples for the study (all 30 patients) have been collected. This is to allow for assay to be conducted at the same time to avoid potential effect of 'time of assay' that may impact data.

All subjects will therefore meet with the CTSC Clinical Research Coordinator for a total of 3 times; at the initiation of the study, at mid-term when the second batch of drug is dispensed and unused drug is returned, and at termination for a second and final blood draw and providing all completed Brief Pain Inventory surveys (5/patient). At the termination of the study, patients will turn in their paper copies of the Brief Pain Inventory questionnaire completed for each week of the study (total 4 weeks). Original data records are important to demonstrate all necessary physical documentation of the study.

## *Non-opioid pramipexole suppresses immune NLRP3 reactivity for pain*

**Pramipexole:** FDA approved drugs that demonstrate an excellent safety profile in humans while also demonstrating the above-noted anti-inflammatory profile could be explored as repurposed drugs for non-opioid pain therapeutics. One such compound that satisfies this profile is pramipexole, which is now documented to reduce inflammation in several preclinical animal models of peripheral inflammatory pain [41]. While this study did not examine rodent pain behaviors, the classic hallmarks of hindpaw edema and neutrophil accumulation were assessed, with pramipexole significantly blunting these inflammatory processes. In a separate study examining brain inflammatory cytokines in mice following low-dose LPS inflammation, IL-1 $\beta$  mRNA levels were blunted following treatment with pramipexole [42]. Pramipexole is well-documented as a preferred dopamine-2/3 (D2/D3) receptor agonist that is FDA approved for alleviating movement disorders in Parkinson Disease and for treating restless leg syndrome, with modest therapeutic outcomes [43-48]. Therefore, based on the documented safety profile of pramipexole, we propose to explore whether it exerts anti-inflammatory (anti- IL-1 $\beta$  actions) resulting in therapeutic pain suppression in people. Our overarching hypothesis is that pramipexole will control clinical pain by suppressing the activation of the TLR4-NLRP3-IL-1 $\beta$  pathway and prevent IL-1 $\beta$  release from peripheral immune cells. These findings have provided the current impetus to examine pain therapeutic drugs targeting immune-related factors either upstream or downstream of IL-1 $\beta$  signaling.

Below is a table and brief description of the planned dispensing pattern. The goal for patients is to achieve improved pain control which will be a score 3 points lower on the BPI scale. However, in some subjects, a requirement of titrating dose-increases will be needed to achieve improved pain control.

### **Week 1**

1 Red at 0.125mg/day

### **Week 2**

1 Red at 0.125 mg/day OR 2 Red to achieve 0.250 mg/day.

### **Week 3**

1 Red at 0.125 mg/day OR 1 green at 0.250 mg/day OR 2 green to achieve 0.5 mg/day.

### **Week 4**

1 Red at 0.125 mg/day OR 2 Red at 0.125 mg/day to achieve 0.250/day, OR 1 green at 0.250 mg/day OR 2 green to achieve 0.5 mg/day, OR 3 green to achieve 0.750 mg/day.

	Week 1	Week 2	Pills needed/ Dispense @ enrollment visit	Week 3	Week 4	Pills needed/ Dispense at midterm
Scenario 1	1 Red	1 Red	14 Red	1 Red	1 Red	14 Red

Scenario 2	1 Red	1 Red	14 Red	1 Red	2 Red	21 Red
Scenario 3	1 Red	2 Red	21 Red	1 Green	1 Green	14 Green
Scenario 4	1 Red	2 Red	21 Red	1 Green	2 Green	21 Green
Scenario 5	1 Red	2 Red	21 Red	2 Green	2 Green	28 Green
Scenario 6	1 Red	2 Red	21 Red	2 Green	3 Green	35 Green

Yellow highlight indicates number of pills at Dispense time.

1st Dispense (week 1)

21 Red pills

2nd Dispense (week 3)

Either 21 Red pills (week 3 subject still at 1 Red)

OR 35 Green pills (any other scenario)

## 13. Data Analysis

**Experimental Design for Phase I (Aim I).** The goal of these experiments is to examine the specific anti-inflammatory mechanisms of pramipexole on PAMP, DAMP and opioid stimulated immune cells, THP-1 cells will be used.

A growing body of evidence supports that repeated opioid exposure triggers TLR4-NLRP3-IL-1 $\beta$  activation and release, which may underlie the development of opioid-induced prolongation of pain and hyperalgesia [16, 28, 29, 39]. THP1 cells are characterized to respond to opioid stimulation by potentiating NFkB [56], and naloxone, a known antagonist at the mu opioid receptor, also blocks TLR4 activation [17, 33-35]. Indeed, naloxone prevents LPS-induced NLRP3 complex formation (NLRP3 + ASC) in THP-1 cells [49]. Results from these experiments could lead to (a) further support that pramipexole is a viable alternative to opioid as a pain therapeutic, and/or (b) co-administration of opioid compounds with pramipexole. The implications are far reaching. To capture TLR4 immune cell activation by distinct mechanisms, PAMPs, DAMPs or opioids, THP-1 cells will be stimulated with either LPS, HMGB1 (a DAMP) or an opioid compound (either beta-endorphins or morphine). Increasing doses of pramipexole will be given, and levels of IL-1 $\beta$  will be analyzed. In addition, cell supernatant and lysates will be collected to evaluate protein and mRNA for TLR4, p38, NFkB, NLRP3, Caspase-1, which is an enzyme activated only after NLRP3 complex formation with ASC that is required for mature IL-1 $\beta$  release, as well as the proinflammatory cytokines, IL-1 $\beta$ , TNF- $\alpha$  and HMGB1, and IL-10

**Statistical Analysis.** The experimental design is 2 (vehicle vs. drug) X 4 (TLR4 stimulants) X 6 (doses of pramipexole), and therefore will require a 3-way repeated measure ANOVA (using IBM SPSS Statistics version 24 (IBM; RRID:SCR\_002865). All biological wells will be conducted in triplicate.

**Experimental Design for Phase II (Aim II).** At the time of consent, all patients will be under standard pain treatment and will be randomized into two groups: (1) patients

